1. PURPOSE OF STUDY

The aim of this randomized controlled trial is to examine the effectiveness of newly developed, theoretical-based graphic messages at preventing future vaping use among African American and Latino adolescents. The images have been iteratively tested in a user-design model and incorporates four main theoretical constructs: health reward, financial reward, self-efficacy, and social norms. We will assess pre- and post-exposure reactions on likelihood of future vaping among African American and Latino adolescents (n=360).

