students in a Title I school district in New Jersey (n=963; 66% Latinos, 37% White, and 36% African Americans) found a prevalence of 19% (compared to 6% for cigarettes) and 55% of students were susceptible to future vaping (no differences by race and ethnicity) (Tercyak et al., 2021). Despite the adverse health effects, high prevalence, and high susceptibility of future vaping among AYAs, there is a lack of effective messages and communication channels to prevent initiation. Overcoming the burden of vaping among AYAs demands affordable, accessible, and effective preventive solutions.

To date, we know little about whether messages can prevent vaping among AYAs and, if so, what messages and delivery formats may be most effective. One study found that chemical and anti-industry warning messages on television advertisements reduce intention to purchase e-cigarettes (Sanders-Jackson et al., 2015). Another study found that addiction warnings increase perceived harms and addictiveness of e-cigarettes and decrease thoughts about vaping, but only when these warnings were text-based – not on print advertisements (Mays et al., 2016). One limitation of both studies is the lack of representation of Latino and African American AYAs. This leaves a substantial gap in communication research for vaping prevention among racial and ethnic minority groups. As the adolescent vaping epidemic continues to grow, there is an urgent need to develop, test, and implement messages and communication channels for vaping prevention.

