4. STUDY DESIGN

This study is a randomized controlled trial (RCT) with a heterogenous sample of 360 African American and Latino adolescents (ages 12-17) who do not vape; equal representation of Latinos and African Americans (180 African American adolescents and 180 Latino adolescents). After completing a preliminary baseline survey, participants will be randomized in equal numbers and representation to receive one of four (4) theoretical-based graphic messages: 1) Financial Reward, 2) Health Reward, 3) Self-efficacy, and 4) Social Norms. These graphic messages were developed in a previous research phase (STUDY00005312) using participatory research methods. See Appendix for the messages. We will assess pre- and post-exposure measures on the susceptibility of future vaping-use among African American and Latino adolescents.

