8. STUDY PROCEDURES

Once parents'/guardians' permission and adolescent's assent has been obtained, participants (n=360) will complete an individual baseline assessment on sociodemographic characteristics and susceptibility to future vaping. The survey will be hosted in REDCap, a secure, web-based system that has user-level access control. Each participant will receive a unique username and password to access the survey. At the end of the baseline assessment, participants will be randomized in equal number and representation to receive one of four (4) graphic messages: 1) health reward, 2) financial reward, 3) self-efficacy, and 4) social norms. The appropriate graphic message, available in English and Spanish, will be displayed in REDCap. Participants will be instructed to view the graphic messages carefully on their devices (e.g., desktop, laptop, tablet, and/or smartphone) and for as long as they wish. We will assess immediate post-exposure measures on susceptibility to future vaping (primary outcome). Study measures on susceptibility to future vaping are comprised of valid items derived from out and others' research. We will assess three items: (1) Are you curious about using e-cigarettes (vaping)?; (2) Do you think that you will use e-cigarettes (vaping) in the next 12 months?; and (3) If one of your best friends were to offer you an e-cigarette, would you use it? Responses include 1= definitely not, 2= probably not, 3= probably yes, 4= definitely yes. Participants will receive \$25 gift card for their time at the end of the assessment.

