10. POTENTIAL BENEFITS TO SUBJECTS

Participation in this study may prevent subjects from vaping. Moreover, this study will examine the effectiveness of newly designed, theoretical-based graphic messages at preventing future vaping use among African American and Latino adolescents.

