17. DATA ANALYSIS PLAN

We first will perform descriptive statistics to evaluate randomization success, nonresponses, and missing data. Mean and median will be presented for continuous variables, and frequencies will be presented for categorical variables. The outcome measures will be defined as (1) a binary variable of susceptibility to future vaping (0= definitely not, 1= probably not, probably yes, definitely yes) to ease interpretation of results, and (2) the overall susceptibility score aggregating three items. Bivariate analyses will be performed, followed by multivariable modeling to compare different message groups. Logistic regression model and the analysis of covariance (ANCOVA), respectively, will be performed to control for potential confounding, and inflated type I error rate will be adjusted in multiple testing. We will also assess differences within messages by theoretical construct (reward, self-efficacy, and social norms). **Power Analysis.** The goal of this pilot analysis is to provide preliminary data for future studies, including the possible effect size. Using the ANCOVA analysis for the power calculation, we expect the effect size to be 1.05 (standardized mean difference in the aggregated score) between message groups.

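### The aim is whether the messages prevent vaping, but all four arms receive an anti-vaping message, so randomisation can show only whether the messages differ

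*Combined protocol and SAP*

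**What the plan says.** - **Aim.** Section 1 says the trial will "examine the effectiveness of newly developed, theoretical-based graphic messages at preventing future vaping use among African American and Latino adolescents". Section 10 repeats it in its second sentence: "this study will examine the effectiveness of newly designed, theoretical-based graphic messages at preventing future vaping use".
- **Question behind the aim.** Section 2 says little is known about "whether messages can prevent vaping among AYAs and, if so, what messages and delivery formats may be most effective". That is two questions: do messages work at all, and which work best.
- **Design.** Section 4 says "participants will be randomized in equal numbers and representation to receive one of four (4) theoretical-based graphic messages": financial reward, health reward, self-efficacy and social norms. Section 8 and the Appendix list the same four. No neutral or no-message group is described.
- **Outcome.** Under Section 8, three susceptibility items are asked at baseline and again straight after the message is viewed. The immediate post-exposure measure is primary. Participants have never used e-cigarettes (Section 5), and no later follow-up is described.
- **Analysis.** Section 17 plans bivariate analyses, "followed by multivariable modeling to compare different message groups", using logistic regression and ANCOVA. Its one expected effect size, a standardised mean difference of 1.05, is also between message groups. It adds: "We will also assess differences within messages by theoretical construct".
- **Purpose of the estimate.** Section 17 also says: "The goal of this pilot analysis is to provide preliminary data for future studies, including the possible effect size".

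**The concern.** The aim asks for the effect of the messages against not having seen them. The randomised comparison sets one active message against another, which answers only part of the second question in Section 2 and none of the first.

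Two readings of the results would be unsafe. If the arms do not differ, the messages may be equally helpful, equally useless or equally harmful. If they do differ, content matters, but the better message has not been shown to beat no message.

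A claim of effectiveness could then rest only on pre-post change. That is measured by repeating the same three items directly after an overt anti-vaping message, so it mixes any message effect with the effects of being asked again and of giving the answer that seems wanted.

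The effect size for future studies is affected too. The randomised data yield a message-versus-message difference, which cannot size a later trial of a message against no message.

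**Working it through.** **1. The plan's own figures.** N = 360 over four equal arms gives 360/4 = 90 per arm. Section 17 states no alpha or power, so 360 cannot be reproduced. With assumed two-sided alpha 0.05, n per arm = 2(z_α + z_power)²/d². At d = 1.05 this is 2(1.960 + 0.842)²/1.1025 = 14.2, so 15 per arm at 80% power, and 20 at 90%. What matters here is that 1.05 is a between-message difference; the plan gives no figure for message against no message.

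**2. What the model can estimate.** Write the post-exposure score in arm j as

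Y = μ + δ + τ_j + β × baseline + error,

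where δ is the effect shared by all messages and τ_j is the departure of message j from it. Every between-arm contrast is (δ + τ_j) − (δ + τ_k) = τ_j − τ_k. The shared effect δ drops out and cannot be separated from μ. In the logistic model a shift common on the log-odds scale is likewise absorbed by the intercept. A larger sample does not change this.

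Direction is lost in the same way. If two messages have effects of −0.5 and 0 SD against no message, they differ by 0.5 SD. If their effects are 0 and +0.5 SD, they also differ by 0.5 SD. The trial data look alike, yet in one case a message helps and in the other a message harms.

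**3. Numerical check.** Rejection rates at alpha 0.05 with 90 per arm:

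| Effect common to all four messages | Test | Simulated trials | Rejected |
|---|---|---|---|
| −0.5 SD | ANCOVA, r = 0.7 | 4,000 | 4.8% |
| 0 | ANCOVA, r = 0.7 | 4,000 | 4.5% |
| +0.5 SD | ANCOVA, r = 0.7 | 4,000 | 4.8% |
| 0 | one-way F | 20,000 | 5.0% |
| 0.5 SD reduction | one-way F | 20,000 | 5.2% |
| 1.05 SD reduction | one-way F | 20,000 | 4.9% |

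The departures from 5% are simulation noise: the standard error is √(0.05 × 0.95/4,000) = 0.34 percentage points for the ANCOVA rows.

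**4. Can pre-post change fill the gap?** Sections 1 and 4 promise pre- and post-exposure measures, but Section 17 names no test, contrast or interpretation for the change. Its remark on differences within messages could mean change within each arm, or a regrouping that merges the two reward messages.

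The following is illustration only, for a test the plan does not specify and with assumed drift and correlation r. With unit SD at both times, the SD of change is √(2(1 − r)). In an arm of 90, z = drift × √90/√(2(1 − r)). For a drift of 0.2 SD at r = 0.7, z = 0.2 × 9.487/0.775 = 2.45, and the chance of nominal significance is Φ(2.45 − 1.96) = 69%. With no message effect at all:

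| Drift from re-asking or demand | r = 0.5 | r = 0.7 | r = 0.8 | r = 0.9 |
|---|---|---|---|---|
| 0.1 SD | 16% | 23% | 32% | 56% |
| 0.2 SD | 48% | 69% | 85% | 99% |

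The normal model ignores floor effects, which are possible in never-users.

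**The case against.** Comparing active messages is a legitimate pilot design, and the comparison is valid for relative effects. Section 1 itself goes on to say that pre- and post-exposure reactions will be assessed, so the protocol never promises a randomised contrast with no message. Section 17 calls the work a pilot, and no later message-versus-nothing trial is described; for a later comparison of messages, the planned estimate is the right one. The 5% rejection rates follow from the nature of a between-arm test, and the drift percentages rest on assumed values.

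Much of this stands. The between-message analysis is not biased, pre-post change is some evidence, and the remark about sizing applies only if the later trial has a no-message arm. The simulation confirms the algebra and says nothing about this trial's data. The drift table shows only what could happen, and the conclusion does not need it.

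None of it closes the gap. Sections 1 and 10 state effectiveness at prevention without a pilot qualification. The pre-post change that would have to support that aim has no comparator and no specified analysis. Rewording being cheap does not make the present aim answerable.

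**Conclusion.** The concern holds. Under any result, the average effect of the messages, which is what the aim asks about, has no controlled estimate in this design. The planned between-arm test rejects about 5% of the time whether all four messages help equally, do nothing or harm equally, and sample size cannot change that. This rests on the design as documented (four active arms and no control), not on an assumed effect size. The only evidence on the average effect is an uncontrolled pre-post change with no stated analysis. Separately, immediate stated susceptibility does not support a claim about vaping prevented. The comparison of messages with one another remains valid. The aim should be corrected before results are interpreted.

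**What to change.** Restate the aim in Section 1 and in the second sentence of Section 10, and align Section 17. For example:

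> The trial estimates the relative immediate effect of four graphic messages on susceptibility to vaping among adolescents who have never used e-cigarettes. Pre-post change within and across arms is reported descriptively with confidence intervals. No claim of effectiveness against no message, or of prevention of vaping, will be made.

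The cost is wording and a narrower claim; participants, arms and the between-message models are unchanged. The first sentence of Section 10, on possible benefit to participants, should be read for consistency with the new aim.

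If an absolute effect is wanted, a control arm is an optional design trade-off. One form is five arms of 72 (36 African American and 36 Latino each) at N = 360, with the fifth seeing a neutral non-vaping graphic. Pooled messages against control would be tested first, then each message against control by Dunnett. At two-sided alpha 0.05 and 80% power, unadjusted for baseline, the detectable differences are:

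- pooled messages against control (288 v 72): 0.37 SD;
- each message against control (72 v 72, Dunnett critical value 2.45): 0.55 SD;
- message against message: 0.47 SD instead of 0.42 SD, or 0.59 instead of 0.52 SD with Bonferroni for six pairs.

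Baseline adjustment multiplies each by √(1 − r²). At an assumed r = 0.7 that is 0.71, so 0.37 and 0.55 SD become about 0.26 and 0.39 SD. This option also needs a protocol amendment, one more REDCap branch, and a neutral graphic in English and Spanish.

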2. BACKGROUND AND RATIONALE

Although conventional cigarette smoking has markedly declined over the past several decades among adolescents (ages 12 to 17), there has been substantial increases in the use of emerging tobacco products among these populations in recent years (Wang et al., 2018). From a product initially marketed as a smoking cessation aid, e-cigarette use, or vaping, rose 900% between 2011 and 2015 among adolescents (from 3% to 27%) and is now two to three times more common among adolescents than among adults (Wang et al., 2018). Vaping products have completely transformed the landscape of nicotine use in youth, combining advanced technology, attractive design, and flavors (now available via online sources), fueled by aggressive marketing and social media promotion (Huang et al., 2019; Kim et al., 2020).

While e-cigarettes *may* support smoking cessation (Hartmann-Boyce et al., 2016; Kalkhoran & Glantz, 2016; Malas et al., 2016), there is robust evidence that exposure to nicotine during adolescence and young adulthood is not only associated with increased rates of use of other substances (Kandel & Kandel, 2014), but also that such use has long-term effects on the developing brain (Yuan, 2015). Chemical and heavy metal exposure from e-cigarettes, added flavorings, and risk of acute injuries and toxicity are a public health concern (Rubinstein et al., 2018). Vaping has been connected to 2,807 lung injury cases and 68 deaths in the US (as of November 2019) (Centers for Disease Control, 2020) and should be considered an increasing public health concern.

There is an urgent need to prevent vaping among adolescents. Adolescence is a period characterized by tobacco-use initiation, experimentation, and progression to long-term addicted behaviors (Sussman & Arnett, 2014; Thompson et al., 2018). Moreover, adolescence offers a critical window for prevention and cessation interventions to produce long-term reductions in tobacco-related morbidity and mortality (Jha et al., 2013; Pirie et al., 2013). In a cross-sectional survey looking at the current vaping prevalence in a diverse sample of 7th, 9th, and 11th grade

students in a Title I school district in New Jersey (n=963; 66% Latinos, 37% White, and 36% African Americans) found a prevalence of 19% (compared to 6% for cigarettes) and 55% of students were susceptible to future vaping (no differences by race and ethnicity) (Tercyak et al., 2021). Despite the adverse health effects, high prevalence, and high susceptibility of future vaping among AYAs, there is a lack of effective messages and communication channels to prevent initiation. Overcoming the burden of vaping among AYAs demands affordable, accessible, and effective preventive solutions.

To date, we know little about whether messages can prevent vaping among AYAs and, if so, what messages and delivery formats may be most effective. One study found that chemical and anti-industry warning messages on television advertisements reduce intention to purchase e-cigarettes (Sanders-Jackson et al., 2015). Another study found that addiction warnings increase perceived harms and addictiveness of e-cigarettes and decrease thoughts about vaping, but only when these warnings were text-based – not on print advertisements (Mays et al., 2016). One limitation of both studies is the lack of representation of Latino and African American AYAs. This leaves a substantial gap in communication research for vaping prevention among racial and ethnic minority groups. As the adolescent vaping epidemic continues to grow, there is an urgent need to develop, test, and implement messages and communication channels for vaping prevention.

3. ADMINISTRATIVE ORGANIZATION

The University of Rochester Medical Center (URMC) is recognized nationally and internationally for its excellence. The URMC schools and researches support and work with lines of research on contemporary parameters that acknowledge the need for a translational approach, traversing different realities. The existing structure, both human and material resources, was prepared to collaborate with making results available to the community quickly and effectively. The work developed and the structure existent for research attracts about 3,000 students, professionals, and researchers interested in joining leading-edge scientific studies and health activities, related to common or rare diseases. At the same time, patients feel confident in seeking the necessary assistance in their services to preserve and improve their health.

Scientists research different topics and areas to improve care and make new treatments available to patients faster. "Investigating Cancer and Improving Care," "Discovering New Pathways to the Molecular Basis of Human Diseases," "Combating Infections and Vaccines Research," "Leading the way to find new treatments for brain diseases," "Keeping the body moving," and "Making children healthier and happier" are examples of URMC investment. To carry out all this work, the University of Rochester School of Medicine and Dentistry has received, in the last five years, financial resources that amount to more than the US \$ 1.18 billion. The investment in biomedical research, financing federal entities, places the URMC in a prominent position (26th) among the various medical centers in the USA. The use of advanced and comprehensive methodologies resulted in the Clinical and Translational Sciences Award from the National Institutes of Health. The effort generates the receipt of funds continuously totaling US\$ 86 million, in addition to a US\$ 19 million grant for integrating the coordination of the top 50 academic medical centers in the country that are part of the Clinical and Translational Science Awards Program.

Several departments and centers work individually and jointly to achieve high-quality results. Among the Departments, the Public Health Sciences (PHS) works to improve health and health care among diverse populations through research, learning, and community partnerships. The research fields explored have several objects, ranging from childhood to older ages, considering food, environment, and everything that involves human health and can impact the individual and the population in general. For this, there are six important programs (Epidemiology and Health Services Research; Master's program in Public Health, Epidemiology; Clinical Investigations; and Health Services Research). PHS research is diverse, including research in behavioral interventions (e.g., smoking research program), environmental health (e.g., etiology of environmentally induced illnesses), maternal child health (e.g., racial/ethnic disparities in pregnancy outcomes), global health (e.g., improving linkage to and retention in HIV continuum of care in China), nutrition (e.g., infant feeding), and health policy and outcomes (nursing home policies that impact the quality of care for the elderly). Population's priorities and concerns, including the needs of minority and underserved communities, define PHS research.

Finally, an important highlight should be given to the Comprehensive Area-Wide Smoking Cessation Program Available through the Center for Community Health & Prevention. UR Medicine provide free smoking cessation counseling sessions for UR Medicine patients. The University of Rochester's experience in this field and the existing structure can be added to other outreach and research activities for the prevention of all smoking-related illnesses.

4. STUDY DESIGN

This study is a randomized controlled trial (RCT) with a heterogenous sample of 360 African American and Latino adolescents (ages 12-17) who do not vape; equal representation of Latinos and African Americans (180 African American adolescents and 180 Latino adolescents). After completing a preliminary baseline survey, participants will be randomized in equal numbers and representation to receive one of four (4) theoretical-based graphic messages: 1) Financial Reward, 2) Health Reward, 3) Self-efficacy, and 4) Social Norms. These graphic messages were developed in a previous research phase (STUDY00005312) using participatory research methods. See Appendix for the messages. We will assess pre- and post-exposure measures on the susceptibility of future vaping-use among African American and Latino adolescents.

5. INCLUSION AND EXCLUSION CRITERIA

Eligible individuals will 1) self-identify as African American/Black and/or Hispanic/Latino, 2) know how to read and speak English and/or Spanish, 3) be at least 12, but no greater than 17 years old, 4) have never used e-cigarettes, and 5) have access to a device that will be able to connect to the online survey (e.g., desktop, laptop, tablet, and/or smartphone). Exclusion criteria include: 1) not identifying as African American/Black and/or Hispanic/Latino, and 2) using e-cigarettes. Eligibility assessment will be conducted by study staff in the participant's language of preference, either English or Spanish.

